7.2.2.5.2 Clinical chemistry

Clinical chemistry samples will be collected at Screening Visits 1 and 2, Visit 3 and then at 4 week intervals, thereafter, as described in the [\[Laboratory Manual\]](#). Parameters to be measured will include: albumin, alkaline phosphatase, total/fractionated bilirubin, calcium, chloride, creatinine, gamma-glutamyl transpeptidase (GGT), fasting glucose, inorganic

phosphorus, potassium, total protein, ALT/SGPT, AST/SGOT, sodium, C-reactive protein, uric acid, lactase dehydrogenase (LDH), urea (BUN).

In accordance with the deferasirox label, serum creatinine, creatinine clearance, and ALT/SGPT must be assessed in duplicate before the initiation of therapy to establish a reliable pretreatment baseline.

In addition, serum creatinine will be measured weekly for the first four weeks of study drug administration at Visits 4, 5, 6, and weekly after any dose escalations for a duration of four weeks. Serum transaminases, bilirubin, and alkaline phosphatase will be measured two weeks after initiation of treatment or any dose escalations. See [Section 6.1.1](#) These assessments after initiation of treatment and dose escalations may be conducted at a local lab.

Creatinine clearance will be estimated in adults using the Cockcroft-Gault equation and in pediatric patients using the Schwartz formula. This estimate will be provided at each monthly visit and at EOT.

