- [Section 6.4.9](#) Hepatic impairment: New section added, providing guidance to treatment dose modifications for patients with moderate or severe hepatic impairment (Child-Pugh class B or C).
- [Section 6.5.2](#) Premature patient withdrawal / End of treatment: Criteria on when patients must be withdrawn from the study were clarified.

Changes to [Section 7](#) Visit schedule and assessments:

- [Table 7-1](#) Visit evaluation schedule: screening evaluations which could be performed at visit 1 or visit 2 were clarified to reflect the screening assessments planned in the protocol.
- [Table 7-1](#) Visit evaluation schedule and [Table 7-2](#) Laboratory assessment schedule: Corrected to include the visits W108-124 and W160-176 missing from these tables but planned and described in the protocol as part of the 4-weeks between visits schedule during the 5 years study duration.
- [Table 7-2](#) Laboratory assessment schedule: in the “Category” column: The category was updated from “S” (Source document) to “D” (database) for the evaluation “Serum/Urine Pregnancy test” as this assessment is recorded in the database and not only in source document as indicated in the protocol.
- [Table 7-2](#) Laboratory assessment schedule: Liver function tests (serum transaminases, bilirubin, and alkaline phosphatase) are part of the monthly biochemistry panel; additional LFTs are required only at visits 5, 9, 17, 27, 36, 46, 55, 65, 74, 84, and 93 (2 weeks after dose initiation and after each dose escalation); all other visits overlapping with biochemistry tests were deleted in the LFT row, to avoid duplication.
- [Table 7-2](#) Laboratory assessment schedule was amended to separate serum pregnancy from urinary pregnancy testing and to indicate that serum testing is required shortly before treatment initiation and urinary testing at the End of Treatment visit. A corresponding footnote was added in the table legend.
- [Section 7.2.2.3](#) Height and weight: clarified that weight assessment can be done at screening either at visit 1 or at visit 2.
- [Section 7.2.2.5.2](#) Clinical chemistry: clarified that estimated Creatinine clearance is obtained monthly and at EoT (Serum creatinine is obtained more often, per [Table 7-2](#))

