6.4.4 Serum creatinine and Creatinine clearance

Serum creatinine and creatinine clearance will be assessed at Weeks -4 and -2 before initiating therapy and should be monitored during the study as indicated in [Table 7-2](#).

During the treatment period, patients who develop an increase in serum creatinine $\geq 33\%$ above their baseline value (average of visit 1 and 2) resulting in a serum creatinine above the

upper limit of normal, on two consecutive occasions, the dose of the study drug will be reduced to:

- 15 mg/kg if the patient takes 30 mg/kg/day,
- 10 mg/kg if the patient takes 15-20 mg/kg/day,
- 5 mg/kg if patient takes 10 mg/kg/day,
- study drug held if patient takes 5 mg/kg/day of deferasirox

until serum creatinine returns to below the ULN.

In case of a single increase in serum creatinine, the assessment will be repeated in 2 weeks.

If after a dose reduction, a progressive increase in serum creatinine beyond the ULN is observed, a treatment interruption is recommended.

After an interruption, if serum creatinine falls below the age appropriate upper limit of normal range on two consecutive visits, it is recommended to resume therapy at 5 mg/kg/day, and after 1 month, if the serum creatinine increase does not recur, study medication can be doubled at one month intervals in order to return to the initial dose.

Caution should especially be used in patients with creatinine clearance between 40 and less than 60 mL/min, particularly in cases where there are additional risk factors that may impair renal function such as concomitant medications, dehydration, or severe infections.

Deferasirox therapy should be discontinued in case serum creatinine increases > 2 times the age-appropriate ULN or if creatinine clearance decreases < 40 mL/min.

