| Males: Total & free testosterone Females: LH & FSH | D | 7.2.1.3 | | | X | | | | | | | | | X | | | X | | | | X (W36, 64, 88, 116, 140, 168, 192, 220, 244) | X | | | |
| Cortisol | D | 7.2.1.3 | | | X | | | | | | | | | X | | | X | | | | X (W36, 64, 88, 116, 140, 168, 192, 220, 244) | X | | | |
| PK (subgroup) | D | 7.2.5.1 | | | | | | | X | | | | | X | | | X (W24) | | | | | | | | |

Visit numbers highlighted in gray in the table above indicate visits conducted for assessments that may be performed locally. After dose initiation and escalation occurs, the patient will have weekly assessments of serum creatinine. Assessments for serum transaminases, bilirubin, and alkaline phosphatase will be completed 2 weeks following dose initiation and escalation.

Blood samples for deferasirox pharmacokinetic assessment will be collected at pre-dose (0 hour), and at 2, and 4 hours at Week 4 (Visit 7). Trough blood samples will be taken at Week 12 (Visit 12) and Week 24 (Visit 15).

* For female patients capable of becoming pregnant serum pregnancy testing should be done within 72 hours prior to treatment start and urine testing at the end of treatment visit (see Section 7.2.2.5.4)

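### The protocol neither provides nor assigns a creatinine clearance estimate at the weekly creatinine checks after treatment start and escalation, so its own clearance stopping limit can go unrecognised for up to three weeks in patients with low baseline clearance

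*Protocol*

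**What the plan says.** Protocol 6.4.4 sets two discontinuation limits joined by an or: "Deferasirox therapy should be discontinued in case serum creatinine increases > 2 times the age-appropriate ULN or if creatinine clearance decreases < 40 mL/min". Neither is tied to a type of visit. The same section has a separate dose-reduction rule. It needs creatinine at least 33% above baseline and above ULN, on two consecutive occasions. The section also asks for caution in patients with clearance from 40 to below 60 mL/min.

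Protocol 7.2.2.5.2 sets the measurement schedule. At treatment start, "serum creatinine will be measured weekly for the first four weeks of study drug administration at Visits 4, 5, 6", with the same weekly pattern for four weeks after any escalation. On the laboratory it says: "These assessments after initiation of treatment and dose escalations may be conducted at a local lab". Clearance is an estimate from the Cockcroft-Gault equation in adults and the Schwartz formula in pediatric patients, and "This estimate will be provided at each monthly visit and at EOT".

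The notes under the laboratory schedule (Protocol 7.1) name only creatinine as the weekly renal measure: "After dose initiation and escalation occurs, the patient will have weekly assessments of serum creatinine". Sections 6.1.1 and 7.1.4 do the same. The Amendment 2 summary agrees with the current text on frequency: "clarified that estimated Creatinine clearance is obtained monthly and at EoT". That amendment also added the clearance discontinuation guidance to 6.4.4.

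**The concern.** The weekly checks are there to detect early renal decline after the drug is started or the dose raised. One of the two stopping limits in 6.4.4 depends on a quantity that the schedule does not supply at most of those checks. A site that follows the text exactly looks at creatinine in Weeks 1 to 3 after a start or escalation and first receives a clearance value at the next monthly visit. If clearance falls below 40 mL/min in between, the protocol's own limit has been met, but nobody is charged with noticing. Some sites may calculate clearance and others may not, so a stopping limit could be applied unevenly across centres.

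This matters only if the clearance limit can be reached before a creatinine rule acts. That is what the working checks.

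**Working it through.** The plan states no figure to reproduce here. The check has three parts.

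**1. Which checks lack a clearance value.** Inputs: the week numbers in Tables 7-1 and 7-2, and the monthly provision in 7.2.2.5.2.

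| Trigger | Weekly checks | Creatinine only | Clearance also provided |
|---|---|---|---|
| Treatment start | Weeks 1, 2, 3, 4 | 1, 2, 3 | 4 |
| Escalation at Week 4 | Weeks 5, 6, 7, 8 | 5, 6, 7 | 8 |
| Escalation at Week 24 | Weeks 25, 26, 27, 28 | 25, 26, 27 | 28 |

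The pattern repeats after each later six-monthly LIC visit at which the dose is raised. Three of every four checks carry no provided clearance. The longest delay runs from the first check to the fourth: 4 − 1 = 3 weeks.

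**2. How large a creatinine rise takes clearance to 40 mL/min.** SAP 5.2 writes out both formulas. With age, sex and body size fixed, clearance is proportional to 1/creatinine in each. Hence

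rise needed = (baseline clearance / 40) − 1.

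| Baseline clearance (mL/min) | Creatinine rise that brings it to 40 |
|---|---|
| 41 | 2.5% |
| 45 | 12.5% |
| 50 | 25% |
| 53.2 | 33% |
| 60 | 50% |
| 80 | 100% |

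Protocol 5.3 excludes clearance of 40 or less on two measurements, so entry just above 40 is possible.

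**3. Whether the creatinine rules act first.**

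- *33% reduction rule.* Setting the rise to 33% gives 40 × 1.33 = 53.2. From any baseline between 40 and 53.2, clearance reaches 40 with a rise too small to meet this rule. The rule also requires a value above ULN, twice running.
- *2 × ULN limit.* Creatinine at clearance 40 equals baseline creatinine × (baseline clearance / 40). If baseline creatinine is at or below ULN and baseline clearance is below 80, this is less than ULN × 80/40 = 2 × ULN. The clearance limit is reached first.
- *Illustration.* The documents give no ULN, so assume baseline creatinine of 0.6 × ULN. Baselines of 60, 80 and 100 mL/min then reach 40 at 0.6 × 60/40 = 0.9, 0.6 × 80/40 = 1.2 and 0.6 × 100/40 = 1.5 × ULN. In the first case creatinine is still within normal, so neither creatinine rule is met. In the other two the rise is 100% and 150% and above ULN, so the reduction rule's criteria are already being met, subject to its second reading.

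**Feasibility.** Weight is recorded every four weeks (Protocol 7.2.2.3). The adult formula is linear in weight, so a 1% to 3% change since the last weighing shifts an estimate of 40 by 0.4 to 1.2 mL/min. Pediatric height is recorded about every six months, so that input may be older.

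**The case against.** The strongest reply is that nothing contradicts anything. Section 6.4.4 states a threshold and 7.2.2.5.2 states when an estimate is routinely supplied. The weekly visits have a stated purpose, creatinine, and feed creatinine rules that work at every check. Amendment 2 added the clearance limit and fixed the monthly frequency together, noting that creatinine is taken more often, which may have been deliberate. That is fair on intent. It does not change the effect: a limit with no visit restriction relies on a value that no one is asked to produce at three of four checks.

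A reader might infer that the clearance limit cannot be applied at the weekly checks. The documents do not support that. Clearance here is arithmetic on a creatinine already measured, with the other inputs on file, and nothing forbids the calculation.

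A reader might also infer that low-weight patients usually reach the clearance limit first. That is not established. The documents give neither ULN values nor a distribution of baseline clearance. They support that it can happen, not how often.

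Three further points stand. At higher baselines the creatinine rules may already be engaged, as the 0.6 × ULN illustration shows. Recruitment had closed by this protocol version, so the first eight weeks were largely or wholly past for enrolled patients. And the creatinine and clearance rows of Table 7-2 were missing from the text I worked from, and the Laboratory Manual was not available. A row or footnote there could settle the matter, although the Amendment 2 summary suggests that the table follows the same schedule.

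**Conclusion.** The point holds as a gap between a stopping limit and the schedule that should serve it. At the checks in Weeks 1 to 3 after start or escalation, the protocol neither provides nor assigns the clearance estimate that 6.4.4 relies on. Recognition of a value below 40 mL/min can be delayed by up to three weeks.

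The exposed patients are those with low baseline clearance. Below about 53 mL/min, the limit can be met without the 33% rule. Below 80 mL/min, with baseline creatinine at or below ULN, it is met before 2 × ULN. These results assume fixed age and body size. The second also assumes baseline creatinine no higher than ULN, which Protocol 5.3 makes likely but not certain, because exclusion needs two raised values.

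How many patients are affected cannot be worked out from the documents. The SAP's baseline table (2.3) has a clearance category below 60 mL/min, which would let the sponsor bound the number. The change is worth making because it closes a safety gap at little cost. The primary analysis does not depend on it.

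**What to change.** Reconcile Protocol 6.4.4 with 7.2.2.5.2 and Table 7-2 so that the clearance estimate is available whenever creatinine is measured, and state who produces it. One way is for the laboratory report or the eCRF to calculate it from each weekly creatinine, central or local, using the latest recorded weight or height. The thresholds and actions in 6.4.4 are not part of this point and stay unchanged.

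The cost is a sentence in 7.2.2.5.2, a matching entry in Table 7-2 and a calculation. No new sample or visit is needed. There are some downsides. There will be more values to review, some from local laboratories, whose results would have to reach whoever does the calculation. For pediatric patients the height used may be up to about six months old, so the text should say which height applies.

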7.2.2.5.3 Urinalysis

Urinalysis samples will be collected at Screening Visits 1 and 2, Visit 3 and every week during the first four weeks and then every four weeks thereafter. A midstream, second voided morning urine sample will be obtained. Specific gravity, pH, blood, glucose, protein, bilirubin, ketones, and leukocyte esterase will be assessed. Microscopic analysis will be performed only in case of positive dipstick. Dipsticks will be supplied by the central lab.

At Screening Visits 1 and 2, a urine sample (at least 15 ml) will be collected and sent to the central laboratory for urinary protein/creatinine ratio to assess the eligibility of the patient. In addition, urine samples for urinary protein/creatinine ratios will be collected at Visit 3 and then at 4 week intervals, thereafter, as described in the [Laboratory Manual]. First morning void samples must not be used for this analysis. Significant proteinuria is indicated by a urinary protein/creatinine ratio > 0.1 mg/mg.

[figure not shown]
For patients who develop proteinuria or a worsening of pre-existing proteinuria (assessed by a dipstick) at any visit, urine samples must be collected and urine protein assessed by the central laboratory.

7.2.2.5.4 Pregnancy and assessments of fertility

All female patients capable of becoming pregnant will have a pregnancy test (serum β -HCG) at Screening Visit 2. The results of the test must be available prior to initiating treatment with any study medication. Women of child-bearing potential must have a negative serum pregnancy test ≤ 72 hours prior to initiating treatment. Positive pregnancy tests will exclude a patient from participating in this trial.

During the treatment period, urine pregnancy testing will be performed locally if menses are delayed for more than 7 days in a female patient capable of becoming pregnant. A urinary pregnancy test will also be performed at the end of treatment visit.

Study drug must be discontinued in patients who become pregnant during the trial. See [Section 8.4](#) for procedures to report pregnancy.

7.2.2.5.5 Hepatitis Viral tests

Hepatitis Viral testing consists of the following items: Hepatitis B Surface Antibody (Anti-HBs), Hepatitis C Antibody (Anti-HCV), Hepatitis B surface Antigen (HBsAg), Qualitative w/confirmation, HCV PCR (Quantitative). Hepatitis Viral testing will be conducted at Screening Visit 1 to assess trial eligibility.

7.2.2.6 Cardiac assessments

7.2.2.6.1 Electrocardiogram (ECG)

A standard 12 lead ECG will be performed at Screening and annually throughout the study (weeks 52, 104, 156, 208, and 260). Interpretation of the tracing must be made by a qualified physician and documented on the ECG CRF page. Each ECG tracing must be labeled with the study number, patient initials (where regulations permit), patient number, date, and kept in the source documents at the study site. Clinically significant abnormalities present when the patient signed the Informed Consent form must be reported on the Medical History CRF page. Clinically significant findings must be discussed with the Novartis Medical Monitor prior to enrolling the patient in the study. New or worsened clinically significant findings occurring after informed consent must be recorded on the Adverse Events CRF page.

[figure not shown]
7.2.3 Pharmacokinetics

Pharmacokinetic (PK) blood sampling will be performed in 20 study patients at specified time points (as shown in [Table 7-2](#)) at Visits 7, 12 and 15 (weeks 4, 12, and 24). These visits will be scheduled in the morning in order to allow the patient to withhold the dose until the pre-dose/trough PK sample is collected just prior to administration of the dose (approximately 24 hours after the previous dose). The patient must be on treatment without dose adjustment or treatment interruption (for any reason) for at least 4 consecutive days prior to scheduled PK sampling visit. If there has been a dosage change or interruption within 4 days of the visit, no PK blood samples should be collected, and an appropriate comment has to be made on the PK CRF page.

Thirty (30) minutes after the pre-dose/trough PK sampling is performed and the dose is administered, the patient may consume a standard breakfast. The patient may alternatively consume a light breakfast 2 hours prior to the pre-dose/trough PK sampling.

PK blood samples will be taken by either direct venipuncture or an indwelling cannula inserted in a forearm vein or antecubital vein to determine plasma concentrations of deferasirox and its iron complex. Plasma concentrations of deferasirox and its iron complex will be presented in tabular format. AUC_{tau}, C_{max}, and t_{max} may be derived from plasma concentration-time profiles (week 4 only) using WinNonlin® (Pharsight, Mountain View, CA).

Multi-center participation in the PK sub-group will be optional. A total of 20 patients will participate in the PK analysis. Pediatric patients will not participate in the PK subgroup.

7.2.3.1 Pharmacokinetic blood collection and sample processing

Three (3) mL blood samples will be collected at each sampling time into a Vacutainer™ tube containing lithium heparin. Immediately after each tube of blood is drawn, it must be inverted gently several times to ensure the mixing of tube contents with the anticoagulant (avoiding prolonged contact with the rubber stopper). Samples must be cooled immediately by placing the tube upright in a test tube rack sitting in an ice-water bath until placed in the centrifuge. Within 30 minutes of sample draw, the samples are centrifuged at about 5°C for 15 minutes at 2000 g (to be adapted according to the radius of the centrifuge). Within 10 minutes after centrifugation, the upper plasma sample will be transferred into two separate 2 mL, tapered, polypropylene screw-cap tubes (Sarstedt #72.693 or equivalent without a skirted base) labeled as A and B. Each tube must have at least 0.5 mL of plasma and these will be stored frozen at -70°C +/- 15°C within 60 min of collection.

Each sample will be given a unique sample number as indicated in Table 7-3. The exact clock time of dosing, as well as actual sample collection date and time must be captured on the PK CRF pages. Issues with obtaining samples will be noted in the comments field of the documents.

Table 7-3 Pharmacokinetic Log

| Visit | Week | Time | PK collection No. | PK sample No. | Sample volume |
|-------|------|---------------|-------------------|---------------|---------------|
| 7 | 4 | Pre-dose/0 h | 1 | 1 | 3 mL |
| 7 | 4 | 2 h post-dose | 1 | 2 | 3 mL |
| 7 | 4 | 4 h post-dose | 1 | 3 | 3 mL |
| 12 | 12 | Pre-dose/0 h | 2 | 4 | 3 mL |
| 15 | 24 | Pre-dose/0 h | 3 | 5 | 3 mL |

7.2.3.2 PK sample handling and shipping

All deferasirox samples must be labeled and frozen upon collection at -70°C +/- 15°C and kept frozen thereafter. All samples must be carefully packed in suitable packing material containing sufficient dry ice to keep them frozen during shipment. Include a list of all samples, including the study number, date, subject number and time of sampling. Clearly indicate if there are any missing samples. Samples will be sent to [REDACTED] China, for analysis.

7.2.3.3 PK analytical method

Deferasirox and its iron complex in plasma will be measured by [REDACTED] China. Plasma concentrations of deferasirox and its iron complex will be determined by a validated liquid chromatography-tandem mass spectrometry (LC-MS/MS) assay with a lower limit of quantitation of 0.670 µmol/L for deferasirox and 0.314 for its iron complex using 100 µL of plasma.

[REDACTED]

[REDACTED]

7.2.5 Other assessments

7.2.5.1 Health-related Quality of Life

Health-related Quality of Life will be assessed at Visits 3, 25, 44 and 63 (Day 1 and weeks 52, 104 and 156). The objective of the health economic component of the study is to evaluate the change in patient reported outcomes (PROs) using the SF-36 in adult patients and the PedsQL in pediatric patients.

SF-36

The Medical Outcomes Study Short Form 36 (SF-36) is a self-administered questionnaire for adults (greater than 18 years of age) and contains 36 items which measure eight dimensions: Physical functioning (10 items), Role limitation due to physical health problems (4 items), Bodily pain (2 items), General health perceptions (5 items), Vitality (4 items), Social functioning (2 items), Role limitations due to emotional problems (3 items) and General mental health (5 items). There is an additional single item giving information on health change over the past year. Item scores for each dimension are coded, summed and transformed to a scale from 0 (worst possible health state measured by the questionnaire) to 100 (best possible health state). The higher values indicate a better evaluation of health. Two summary scores of physical and mental health can also be calculated and scoring is norm-based, with normative values at 50 and no floor or ceilings. The SF-36 is well-documented in terms of reliability and validity in all available language versions ([Ware and Sherbourne 1992](#)). The SF-36 has a 4 week recall period. The questionnaire will be scored as per the instructions of the developers of the SF-36. In addition, the SF-6D, a utility measure of health states, can be derived from the SF-36 and the scoring for the SF-6D utility values will also be assessed using the scoring methods from the developers.

PedsQL 4.0

The PedsQL™ is a modular approach to measuring health-related quality of life (HRQOL) in children and adolescents. This will be administered to children between the ages of 13 to 18 years. The approach includes both a child self-report and parent proxy-report. The 23-item PedsQL™ Generic Core Scales encompass the essential core domains for pediatric HRQOL measurement: 1) Physical Functioning (8 items), 2) Emotional Functioning (5 items), 3) Social Functioning (5 items), and 4) School Functioning (5 items). The Generic Core Scales are designed to enable comparisons across patient and healthy populations.

Internal consistency reliability of the PedsQL™ was excellent, with alphas for the generic core scales in both self- and proxy-report greater than the 0.70 standard, and alphas for the full 23-item scale approaching 0.90 for self- and proxy-report. Missing data were minimal. Item response distributions were across the full scale range, with no floor effects, and minimal ceiling effects.

The validity of the PedsQL™ Generic Core Scales was demonstrated through known groups comparisons, and correlations with other measures of disease burden. The PedsQL™ self- and proxy-report distinguished between children with and without a chronic health condition, and within the group of children with a chronic condition, between those who did or did not have an overnight hospital visit in the last 12 months. Further, both child self-report and parent proxy-report correlated significantly with the number of days the child was too ill to pursue normal activities, needed someone to care for him or her, missed school in the last month, the number of days the parent missed from work in the last month, and parent-report of problems pursuing their normal work routine and concentrating at work. The PedsQL™ Generic Core Scales are also responsive to clinical change, as demonstrated in field trials.

